## **Scoring Best-Corrected Visual Acuity**

On the BCDVA Assessment Form, the total number of letters read correctly in each row of letters should be written down. Visual acuity will be measured once for each eye, using Chart 1 for the right eye, Chart 2 for the left eye, and Chart 1 for binocular vision testing. After each measurement of visual acuity, the visual score for the visit is calculated. The visual acuity score is defined as follows:

- If 20 or more letters are read correctly at the 4-meter test distance, the visual acuity score is equal to the numbers of letters read correctly at 4 meters, plus 30; or
- If less than 20 letters are read correctly at the 4-meter test distance, the visual acuity score is equal to the number of letters read correctly at 1 meter plus the number at 4 meters: or
- If no letters are read correctly at either the 4-meter distance or the 1-meter distance, the visual acuity score is 0.

# **Count Fingers Visual Acuity**

If visual acuity is so poor that the subject cannot read any of the largest letters at 1 meter (i.e. number of letters read correctly at 1 meter is zero), count fingers vision (CF), the examiner's hand holding 1, 2, or 5 fingers is held steady at a distance of two feet directly in front of the eye being examined. If testing the right eye, the left eye must be occluded by lightly patching with an eye pad or a folded tissue with tape. A light should be shone directly on the hand from behind the patient. The examiner's fingers should be presented in random order and repeated 5 times. Eccentric fixation, if present, should be encouraged. If the subject correctly identifies three of the five presentations, then count fingers (CF) is noted as "yes." If not, the subject should be tested for hand motion vision.

## Hand Motion Visual Acuity

The examiner's hand with all fingers spread out should be extended two feet directly in front of the eye being examined. The fellow eye should be occluded. If testing the right eye, the left eye must be occluded by lightly patching with an eye pad or a folded tissue with tape. A light should be shone directly on the hand from behind the subject. The examiner's hand should be moved in an up and down direction (vertically) or in a side-to-side direction (horizontally) at a constant speed of approximately one back and forth presentation per

second. The subject is instructed that the examiner's hand will be presented, and they will have to respond to the question: "What am I doing with my hand?" This should be repeated five times. Four out of five correct responses indicate that hand motion vision is present. If the subject does not correctly identify four of five, then light perception must be tested.

## **Light Perception and No Light Perception**

Light perception should be tested with an indirect ophthalmoscope in a darkened room. The fellow eye should be well occluded, ideally with a taped tissue behind the trial frame as well as the occlude lens in the trial frame. The indirect ophthalmoscope light should be in focus at 3 feet with the rheostat set at maximum voltage. From a distance of 3 feet, the beam should be directed in and out of the eye being examined at least four times, and the subject should be asked to respond when he or she sees the light. If the examiner is convinced that the subject perceives the light, vision should be recorded as "light perception"; if not, vision should be recorded as "no light perception."

When examiners conclude that the final visual acuity score is totally unreliable because of the subject's decreased mental ability, the visual acuity score must still be entered on the appropriate form.

In order to provide standardized and well-controlled assessments of visual acuity during the study, all visual acuity assessments at a single site must be consistently done using the same lighting conditions and same correction if possible, during the entire study. If the same correction cannot be used (i.e., a subject broke his/her glasses), the reason for the change in correction should be documented.

Note: A clinically significant visual acuity decrease defined as  $\geq 3$  lines (15 ETDRS letters) or from Visit 1 should be evaluated by the Investigator as a potential AE.

# **Slit Lamp Bio microscopy**

Slit lamp bio microscopy will be performed during the study. Observations will be graded as *Normal* or *Abnormal*. Abnormal findings, which are clinically significant, will be described.

# **Cornea Photography**

Details instructions will be provided in the photography manual.

## **Corneal Fluorescein Staining**

The examiner should instill 5  $\mu$ L of 2% preservative-free sodium fluorescein solution into the inferior conjunctival cul-de-sac of each eye. Alternatively, corneal staining can be assessed using 1.0 mg sodium fluorescein strips. After moistening the tip of the strip with sterile buffered saline, the excess is shaken into a waste bin with a sharp flick. The lower lid is then

pulled down and the flat end of the tip should be gently applied to the inferior tarsal conjunctiva with the intent of not inducing reflex tearing and instilling a very small volume of dye.

[figure not shown]
The subject will be instructed to blink naturally several times without forced closure of the eyelid to distribute the fluorescein. To achieve maximum fluorescence, the examiner should wait at least two minutes after instillation before evaluating corneal fluorescein staining. A Wratten #12 yellow filter will be used to enhance the ability to grade fluorescein staining. The staining will be graded with the modified Oxford Grading Scale.

#### **Modified Oxford Grading Scale**

The examiner compares the overall appearance of the patient's corneal staining with the reference figure (below) and selects the appropriate grade that best represents the state of corneal staining.

For subjects that progress to Stage 2, graders will assess the following:

- Lesion size
- Is any residual staining present (Yes/No)?
- If residual staining is present, is the staining persistent (Yes/No)?

# The Grade 0 corresponds to none staining dots

## **Corneal Sensitivity**

#### **Cochet-Bonnet Aesthesiometer**

Corneal sensation is measured in the affected eye of the patient at all applicable visits using a Cochet Bonnet aesthesiometer. The measurements taken from the affected eye are as follows:

Sensitivity in each of the 4 quadrants of the cornea:

- Superior nasal (cm)
- Inferior nasal (cm)
- Superior temporal (cm)
- Inferior temporal (cm)

Steps for using the handheld aesthesiometer:

Note: Cochet Bonnet aesthesiometer measurements MUST be performed prior to administration of Topical Anesthesia

- Sterilize the filament, by wiping only the tip with an alcohol pad, do not wipe the entire length of the filament or pull on the filament.
- Extend the filament to full length of 6 cm.
- Perform sensitivity in each of the 4 quadrants of the cornea:
- Superior nasal (cm)
- Inferior nasal (cm)
- Superior temporal (cm)
- Inferior temporal (cm)
- Retract the filament incrementally in 0.5 cm steps until the patient can feel its contact.
- Record the length (NOTE: The shorter the length indicates decreased sensation.)
- Compare the fellow eye cornea.
- Repeat steps 1-4 in each quadrant: superior nasal, inferior nasal, superior temporal, and inferior nasal.
- Sterilize the filament tip by gently wiping with an alcohol pad and retract back into the device to protect it from damage.

For Stage 1 subjects, corneal sensitivity is defined as the mean of the 4 quadrants (four measurements)

## **Intranasal Examination**

Qualified subjects for the study must undergo an intranasal exam to make the final eligibility determination (e.g., severe nasal airway obstruction such as, severe septal deviation or inferior turbinate hypertrophy, or vascularized polyp seen on examination are reasons for exclusion). To monitor nasal mucosal integrity during the study for subject safety, an examination of the nasal cavities via an intranasal exam will be performed at Visit 1 (after all other screening procedures have been completed). This examination will be performed by an Ear Nose and Throat (ENT) specialist, otolaryngologist or other suitably qualified medical practitioner (i.e. one who has been trained to perform intranasal exam). Still images or video may be captured. The procedure used for the intranasal exam can be conducted either by endoscopic examination or nasal specula.

# Schirmer's Test without Anesthesia

- 1. Excess moisture in the inferior fornix is gently removed with a sponge spear.
  - Schirmer's strips (35 mm x 5 mm size filter paper strip) will be placed in each eye at the junction of the middle and lateral thirds of the lower eye lid.
  - Under ambient light, the subject will be instructed to look forward and to blink normally during the test. The test should be performed in a room with no direct air or sunlight on the subject's face.
  - The Schirmer's strips should remain in place until five minutes have elapsed or both strips have reached maximum score.
  - After five minutes, strips will be removed from both eyes and the amount of wetting will be recorded. The strips should be taped to the source document.

[figure not shown]
# Schirmer's Test with Topical Anesthesia

The Schirmer's test will be performed concurrent with the study drug/placebo nasal spray treatment be used to assess tear production using the following steps:

- 1. Topical anesthetic drops such as 0.5% proparacaine hydrochloride or equivalent should be instilled in both eyes of the subject.
  - The subject will be instructed to keep the eyes gently closed for one minute.

- After opening the eyes and allowing the eyes to recover for approximately one additional minute, excess moisture in the inferior fornix is gently removed with a sponge spear.
- Schirmer's strips (35 mm x 5 mm size filter paper strip) will be placed in each eye at the junction of the middle and lateral thirds of the lower eye lid.
- Under ambient light, the subject will be instructed to look forward and to blink normally during the test. The test should be performed in a room with no direct air or sunlight on the subject's face.
- The Schirmer's strips should remain in place until five minutes have elapsed or both strips have reached maximum score.
- After five minutes, strips will be removed from both eyes and the amount of wetting will be recorded. The strips should be taped to the CRF.

# PAIN VISUAL ANALOG SCALE (VAS)

# NATIONAL EYE INSTITUTE Visual Functioning Questionnaire - 25 (NEI-VFQ-25)

Version 2000

# (SELF-ADMINISTERED FORMAT)

# January 2000

The following is a survey with statements about problems which involve your vision or feelings that you have about your vision condition. After each question, please choose the response that best describes your situation.

Please answer all the questions as if you were wearing your glasses or contact lenses (if any).

Please take as much time as you need to answer each question. All your answers are confidential. In order for this survey to improve our knowledge

about vision problems and how they affect your quality of life, your answers must be as accurate as possible. Remember, if you wear glasses or contact lenses, please answer all of the following questions as though you were wearing them.

#### **INSTRUCTIONS:**

2. In general we would like to have people try to complete these forms on their own. If you find that you need assistance, please feel free to ask the project staff and they will assist you.

 $^{2}$  NEI-VFQ-25 is reproduced here (in part or in its entirety) with permission from the RAND Corporation. Copyright © the RAND Corporation. RAND's permission to reproduce the survey is not an endorsement of the products, services, or other uses in which the survey appears or is applied.

- 3. Please answer every question (unless you are asked to skip questions because they don't apply to you).
- 4. Answer the questions by circling the appropriate number.
- 5. If you are unsure of how to answer a question, please give the best answer you can and make a comment in the left margin.
- 6. Please complete the questionnaire before leaving the center and give it to a member of the project staff. Do not take it home.
- 7. If you have any questions, please feel free to ask a member of the project staff, and they will be glad to help you.

#### STATEMENT OF CONFIDENTIALITY:

All information that would permit identification of any person who completed this questionnaire will be regarded as strictly confidential. Such information will be used only for the purposes of this study and will not be disclosed or released for any other purposes without prior consent, except as required by law

# **Visual Functioning Questionnaire - 25**

PART 1 - GENERAL HEALTH AND VISION

1. In general, would you say your overall health is:

(Circle O	ne)
Excellent	1
Very Good	2
Good	3
Fair	4
Poor	5

2. At the present time, would you say your eyesight using both eyes (with glasses or contact lenses, if you wear them) is excellent, good, fair, poor, or very poor or are you completely blind?

(Circle One)

Excellent	1
Good	2
Fair	3
Poor	4
Very Poor	5
Completely Blind	6

### 3. How much of the time do you worry about your eyesight?

(Circle One)

None of the time	1
A little of the time	2
Some of the time	3
Most of the time	4
All of the time?	5

4. How much pain or discomfort have you had in and around your eyes (for example, burning, itching, or aching)? Would you say it is:

(Circle One)

None	1
Mild	2
Moderate	3
Severe, or	4
Very severe?	5

#### PART 2 - DIFFICULTY WITH ACTIVITIES

The next questions are about how much difficulty, if any, you have doing certain activities wearing your glasses or contact lenses if you use them for that activity.

5. How much difficulty do you have reading ordinary print in newspapers? Would you say you have:

(Circle One)

No difficulty at all	1
A little difficulty	2
Moderate difficulty	3
Extreme difficulty	4
Stopped doing this because of your eyesight	5

6. How much difficulty do you have doing work or hobbies that require you to see well up close, such as cooking, sewing, fixing things around the house, or using hand tools? Would you say:

(Circle One)

No difficulty at all	1
A little difficulty	2
Moderate difficulty	3
Extreme difficulty	4
Stopped doing this because of your eyesight	5
Stopped doing this for other reasons or not interested in doing this	6

7. Because of your eyesight, how much difficulty do you have finding something on a crowded shelf?

(C	ircle One)
No difficulty at all	1
A little difficulty	2
Moderate difficulty	3
Extreme difficulty	4
Stopped doing this because of your eyesight	5
Stopped doing this for other reasons or not interested in doing this	. 6

8. How much difficulty do you have reading street signs or the names of stores?

	(Circle One)
No difficulty at all	1
A little difficulty	2
Moderate difficulty	3

Extreme difficulty	4
Stopped doing this because of your eyesight	5
Stopped doing this for other reasons or not interested in doing this	. 6

9. Because of your eyesight, how much difficulty do you have going down steps, stairs, or curbs in dim light or at night?

(Circle	One)
---------	------

No difficulty at all	1
A little difficulty	2
Moderate difficulty	3
Extreme difficulty	4
Stopped doing this because of your eyesight	5
Stopped doing this for other reasons or not interested in doing this	6

10. Because of your eyesight, how much difficulty do you have noticing objects off to the side while you are walking along?

(Ci	rcle One)
No difficulty at all	1
A little difficulty	2
Moderate difficulty	3
Extreme difficulty	4
Stopped doing this because of your eyesight	5
Stopped doing this for other reasons or not interested in doing this	6

11. Because of your eyesight, how much difficulty do you have seeing how people react to things you say?

(Circle One) (Circle One) (Circle One)

A little difficulty	2
Moderate difficulty	3
Extreme difficulty	4
Stopped doing this because of your eyesight	5
Stopped doing this for other reasons or not interested in doing this	6

12. Because of your eyesight, how much difficulty do you have picking out and matching your own clothes?

	(Circle One)
No difficulty at all	1
A little difficulty	2
Moderate difficulty	3
Extreme difficulty	4
Stopped doing this because of your eyesight.	5
Stopped doing this for other reasons or not interested in doing this	6

13. Because of your eyesight, how much difficulty do you have visiting with people in their homes, at parties, or in restaurants?

(C	ircle
No difficulty at all	1
A little difficulty	2
Moderate difficulty	3
Extreme difficulty	4
Stopped doing this because of your eyesight	5
Stopped doing this for other reasons or not interested in doing this	.6

14. Because of your eyesight, how much difficulty do you have going out to see movies, plays, or sports events?

(Circle One)

One)

No difficulty at all	1
A little difficulty	2
Moderate difficulty	3
Extreme difficulty	4
Stopped doing this because of your eyesight	5
Stopped doing this for other reasons or not interested in doing this	6

15. Are you currently driving, at least once in a while?

(Circle On	e)	
Yes	1	Skip To Q 15c
No	2	

15a. IF NO: Have you never driven a car or have you given up driving?

(Circle One)

Never drove...... 1 Skip To Part 3, Q 17

Gave up..... 2

15b. IF YOU GAVE UP DRIVING: Was that mainly because of your eyesight, mainly for some other reason, or because of both your eyesight and other reasons?

(Circle One)

Mainly eyesight	1	Skip To Part 3, Q 17
Mainly other reasons	2	Skip To Part 3, Q 17
Both eyesight and other reasons	3	Skip To Part 3, Q 17

Confidential

68

#### 15c. IF CURRENTLY DRIVING: How much difficulty do you have driving during the daytime in familiar places? Would you say you have:

(Circle One	<del>)</del>
No difficulty at all	1
A little difficulty	2
Moderate difficulty	3
Extreme difficulty	4

16. How much difficulty do you have driving at night? Would you say you have:

(Circle One)

No difficulty at all	1
A little difficulty	2
Moderate difficulty	3
Extreme difficulty	4
Have you stopped doing this because of your eyesight	5
Have you stopped doing this for other reasons or are you not interested in doing this	6

16A. How much difficulty do you have driving in difficult conditions, such as in bad weather, during rush hour, on the freeway, or in city traffic? Would you say you have:

(Circle One)

No difficulty at all	1
A little difficulty	2
Moderate difficulty	3
Extreme difficulty	4
Have you stopped doing this because of your eyesight	5

#### 

#### PART 3: RESPONSES TO VISION PROBLEMS

The next questions are about how things you do may be affected by your vision. For each one, please circle the number to indicate whether for youthe statement is true for you all, most, some, a little, or none of the time.

#### (Circle One On Each Line)

READ CATEGORIES:	All of the time	Most of the time	Some of the time	A little of the time	None of the time
17. Do you accomplish less than you would like because of your vision?	1	2	3	4	5
18. Are you limited in how long you can work or do other activities because of your vision?	1	2	3	4	5
19. How much does pain or discomfort in or around your eyes , for example, burning, itching, or aching, keep you from doing what you'd like to be doing? Would you say:	1	2	3	4	5

For each of the following statements, please circle the number to indicate whether for you the statement is definitely true, mostly true, mostly false, or definitely false for you or you are not sure.

(Circle One On Each Line)

	ſ	Definitely True	Mostly True	Not Sure	Mostly False	Definitely False
20.	l stay home most of the tir because of my eyesight		2	3	4	5
21.	I feel frustrated a lot of the time because of my eyesight.		2	3	4	5
22.	I have much less control over what I do, because of my eyesight		2	3	4	5
23.	Because of my eyesight, I have to rely too much on what other people tell me	1	2	3	4	5
24.	l need a lot of help from others because of my eyesight	1	2	3	4	5
25.	I worry about doing things that will embarrass myself or others , because of my eyesight.	Ē	2	3	4	5

Appendix 1 Schedule of Visits and Measurements	

# 1 Synopsis

Protocol Title:	A Phase 2, Multicenter, Randomized, Controlled, Double-Masked, Clinical Trial to Evaluate the Efficacy and Safety of OC-01 (varenicline) Nasal Sprayin Subjects with Neurotrophic Keratopathy (the Olympia Study)
Protocol Number:	OPP-102
Investigational Product:	OC-01 (varenicline) Nasal Spray:  • 1.2 mg/mL
Study Objective:	The objective of this study is to evaluate the safety and effectiveness of OC-01 (varenicline) nasal spray as compared to placebo nasal spray for mean change from baseline in corneal fluorescein staining in subjects with Stage 1 (corneal epithelial hyperplasia/punctate keratopathy) neurotrophic keratopathy (NK) in one or both eyes.
Treatment Assignment	100 subjects will be randomized in a 1:1 into one of two treatment groups:  • 1.2 mg/mL  • Placebo (vehicle)
Sample Size and Power	
Randomization and Stratification	The randomization will be stratified by:  • Pre-procedure (Baseline) non-anesthetized Schirmer's score (≤ 5, > 5) measured at the screening/randomization visit.
Efficacy Endpoint	Primary Endpoint:  • Mean change from baseline in corneal fluorescein staining in subjects with Stage 1 NK at Week 8.
	Secondary Endpoint  • Mean change from baseline in ETDRS visual acuity at Week 8
	
 
Percent of subjects who achieve ≥ 3 lines (15 letters) of improvement in ETDRS visual acuity at Week 8
 
Percent of subjects who achieve complete resolution of corneal staining (defined as complete resolution of corneal staining (0 mm lesion and no residual staining) in subjects with Stage 1 NK at Week 8.
 
Percentage (%) of subjects that progress to Stage 2 Persistent Epithelial Defect (PED) NK at Week 8.
 
Mean change from in improvement in corneal sensitivity at Week 8.
 
Mean change from baseline in corneal fluorescein staining in subjects with Stage 2 NK at Week 8.
 

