# 5.4. Exclusion Criteria

#### Subjects must not:

- 1. Have Stage 2 or Stage 3 NK affecting one or both eyes.
- 2. Have ocular graft versus host disease or Stevens-Johnson syndrome.
- 3. Have any active ocular infection (COVID-19 conjunctivitis, bacterial, viral, fungal, or protozoal) or active ocular inflammation not related to NK in the affected eye.

- 6. Be currently receiving autologous serum tears, amniotic membrane, cenegermin, Fresh Frozen plasma or cord blood derived tears.
- 7. Have severe blepharitis and/or severe meibomian gland disease in the study eye.

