# 5.5. Withdrawal Criteria

If at any time during the study the Investigator determines that a subject's safety has been compromised, the subject may be withdrawn from treatment, but will be followed for safety for the duration of the study, unless they refuse to attend follow-up visits.

Additionally, if a subject should progress to Stage 2 NK while receiving the study drug, the subject should remain in the study and receive treatment. If a subject should progress to Stage 3 NK while receiving study treatment, the subject may be withdrawn from treatment at the discretion of the Investigator. The subject will continue to be followed for safety unless the subject refuses to attend the follow-up visits.

A subject may withdraw consent from the study at any time.

The Sponsor and/or the Investigator may discontinue any subject from study treatment for noncompliance or for any valid medical reason during the study (see Section 8.6.2).

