#### Visit 6 (Week 8) - Day 56 ± 2: corneal assessment

- NEI-VFQ-25 questionnaire
- VAS
- Urine pregnancy test (if applicable)

- NK staging per Mackie Criteria
- BCDVA
- Slit lamp biomicroscopy (prior to Schirmer's Test)
- Corneal fluorescein staining (prior to Schirmer's Test)
- Slit lamp (cornea) photography (prior to Schirmer's Test)
- Corneal sensitivity (prior to Schirmer's Test)
- In-vivo Confocal Microscopy (prior to Schirmer's Test) (select centers)
- Intranasal examination
- Schirmer's Test with anesthesia (concurrent with treatment)
- Administration of the study drug/placebo nasal spray (concurrent with Schirmer's test)
- Concomitant medications
- AE query

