Appendix 1 describes the detailed study visits, measurements, and dosing information.

## 5 Primary, Secondary and Exploratory Endpoints

#### 5.1 Primary Efficacy Endpoint

The primary endpoint will be the mean change from baseline in corneal fluorescein staining at Week 8.

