#### 5.3 Exploratory Efficacy Endpoint

- Percent of subjects who achieve ≥ 3 lines (15 letters) of improvement in ETDRS visual acuity at Week 8.
- Percent of subjects who achieve complete resolution of corneal staining will be the exploratory endpoint. Complete resolution of corneal staining will be the exploratory endpoint is defined as complete resolution of corneal staining (0 mm lesion and no residual staining) in subjects with Stage 1 NK at Week 8.
- Percentage (%) of subjects that progress to Stage 2 Persistent Epithelial Defect (PED) NKat Week 8.
- Improvement in corneal sensitivity at Week 8
- Mean change from baseline in corneal fluorescein staining in subjects with Stage 2 NK at Week 8.
- Schirmer's score with topical anesthesia
- Pain visual analog scale (VAS)
- Slit lamp biomicroscopy
- NEI-VFQ-25 Survey

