#### 8 Statistical Hypothesis Testing

Let  $\mu_h$ , and  $\mu_p$  denote the mean change in corneal fluorescein staining from baseline to Week 8 (1.2 mg/mL OC-01 and placebo, respectively) in subjects with Stage 1 NK.

 $H_0$ :  $\mu_h$ - $\mu_p = 0$ 

VS.

 $H_1: \mu_h - \mu_p \neq 0$ 

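### Does the SAP's Stage 1 at Week 8 wording remove subjects who progressed from the primary comparison?

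*SAP*

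**What the plan says.** The SAP synopsis gives the primary endpoint as "Mean change from baseline in corneal fluorescein staining in subjects with Stage 1 NK at Week 8". The Protocol synopsis and Protocol 6.1.1 and 10.1.1 use the same wording. SAP 5.3, like the SAP synopsis, lists an exploratory endpoint, "Mean change from baseline in corneal fluorescein staining in subjects with Stage 2 NK at Week 8". It also defines complete resolution with the phrase "0 mm lesion and no residual staining) in subjects with Stage 1 NK at Week 8".

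The sections that set up the analysis are worded differently. SAP 5.1 reads "The primary endpoint will be the mean change from baseline in corneal fluorescein staining at Week 8", with no stage at all. In SAP 8 the two symbols "denote the mean change in corneal fluorescein staining from baseline to Week 8" for active and placebo; subjects with Stage 1 disease are named afterwards, without a date on the stage. SAP 14.1 assigns the primary endpoint to the per-protocol (PP) population and an analysis of covariance. Protocol 10.2.2 forms that population from ITT subjects with a baseline staining grade of at least 2 and Stage I disease.

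On stage itself, Protocol 5.4 lists among the exclusions "Have Stage 2 or Stage 3 NK affecting one or both eyes". For a subject who reaches Stage 2 on study drug, Protocol 5.5 says that "the subject should remain in the study and receive treatment". Protocol 8.3.1 schedules staining and Mackie staging at Visit 6 (Week 8) with no exception by stage, and progression to Stage 2 is itself an exploratory endpoint in SAP 5.3.

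**The concern.** The primary and the Stage 2 endpoints use the same sentence with one digit changed, so a reader expects the stage to be dated the same way in both. If stage means stage at entry, the Stage 2 endpoint has no subjects. If it means stage at Week 8, the primary endpoint leaves out everyone who progressed.

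The second reading would do harm. Progression happens after randomisation and may depend on treatment. Leaving progressors out removes poor outcomes, and more of them from the arm that does worse, so a real benefit would look smaller. Stage is recorded at Week 8, so such a filter could be programmed. The rule that the SAP prevails over the protocol does not help, because the tension lies within the SAP.

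**Working it through.** **1. Try each reading on each endpoint.**

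| Endpoint | Stage at entry | Stage at Week 8 |
|---|---|---|
| Primary, Stage 1 | All PP subjects | Progressors dropped |
| Complete resolution, Stage 1 | All Stage 1 entrants | A cleared cornea must still be staged as 1 |
| Exploratory, Stage 2 | Nobody, given Protocol 5.4 | Subjects who progressed |

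Stage at Week 8 fits all three phrases literally, so the wording is not impossible to satisfy. It fits the resolution endpoint poorly, because the grading table in Protocol Appendix 2 has no stage for a cleared cornea. The endpoints also need not share one reading. The entry criteria settle the Stage 2 endpoint on their own: it can only concern progressors.

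**2. Ask what Week 8 modifies.** The secondary endpoint in SAP 5.2 closes with the same time phrase and mentions no stage, so there it can only date the change. SAP 8 makes the same link for the primary endpoint: Week 8 belongs to the change and the stage carries no date. The objective in SAP 3 names Stage 1 subjects with no time point, and SAP 4 describes enrolling subjects diagnosed with Stage 1 disease. All of this points to Stage 1 as the enrolled condition and Week 8 as the time of measurement.

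**3. Look for a filter in the operative text.** SAP 5.1 has no stage condition. The visible text of SAP 14.1 names the PP population and the covariates, with no exclusion by Week 8 stage. Protocol 10.2.2 has no Week 8 condition either. An analyst working from these sections includes progressors.

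**4. Size of a misreading, for illustration only.** The visible text gives no effect size, SD or progression rate, so the inputs are assumed. Let non-progressors have the same mean change in both arms, let progressors be D grades worse, and let pP and pA be the progression rates on placebo and OC-01. Including everyone, the arms differ by (pP − pA) × D. Excluding progressors, they differ by 0. The gap between the readings is therefore (pP − pA) × D:

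- 5% v 5%: 0 × D = 0
- 10% v 5%: 0.05 × 1 = 0.05 grade; 0.05 × 2 = 0.10 grade
- 20% v 10%: 0.10 × 1 = 0.10 grade; 0.10 × 2 = 0.20 grade
- 20% v 5%, D = 2: 0.15 × 2 = 0.30 grade

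The loss of numbers alone matters less. With two-sided 5% and 80% power, the detectable difference is (1.960 + 0.842) × √(2/n) SD. That is 0.56 SD at n = 50 per arm, 0.59 at 45 and 0.63 at 40.

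**The case for a change.** The strongest case for a change is that no visible sentence says progressors are included, and that the only reading giving both staining endpoints subjects is the one that damages the primary comparison. A simulation under assumed inputs set power near 80% with 50 PP subjects per arm and 10% placebo progression. Restricting to Stage 1 at Week 8 then left 81–92% of the full estimate and 69–73% power, with type I error at 4.7–5.3% across the scenarios run. One clarifying sentence would cost almost nothing.

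It stands that the synopsis phrase is loose and that selecting on Week 8 stage would be a poor analysis. The rest carries less weight. The simulation sizes a reading that the operative sections do not give. It also takes 50 PP subjects per arm when about 50 per arm are enrolled and the PP population is a subset of them. The illustration above shows no shift when progression is equal in the two arms. Nor can silence be inferred: the text under SAP 9.2.2, 14.3 and 14.4, where population, exploratory analyses and missing data would be dealt with, is not visible in the public copy.

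A related question is what score progressors contribute. The Modified Oxford Grading Scale part of Protocol Appendix 2 adds lesion size and residual-staining items for them, without saying whether the Oxford grade is still taken. SAP 9.11.5 calls for an Oxford grade at Week 8 with no exception by stage, so the natural reading is that the extra items supplement the grade.

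**Conclusion.** No change to the plan is needed. The synopsis phrase is a drafting looseness that the SAP's own endpoint, hypothesis and analysis sections resolve: Stage 1 describes who was enrolled, Week 8 dates the measurement, and progressors stay in the primary comparison. The Stage 2 endpoint is a summary of progressors. It is exploratory, probably rests on few subjects, and has no bearing on the primary result. Tidier wording would read better but would leave the analysis as it is.

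The effect on the primary result under this reading is nil. The 0 to 0.30 grade range applies only if a filter absent from the operative text were added, and it rests entirely on assumed progression rates and severity. The conclusion assumes that the text not visible in the SAP contains no exclusion by Week 8 stage; nothing in the visible text suggests one.
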